8.2.4 Survival follow-up

Following the safety follow-up visit, site staff will contact the patient every 3 months for 2 years and then every 6 months for the next 3 years or until the patient is lost to follow-up or dies. Survival follow-up will determine survival status and record if patients have taken any new anticancer treatments. This contact may be by telephone, E-Mail or other form of communication but must be documented in the source notes.

8.3 Safety assessments

Safety assessments will be performed routinely using vital signs, physical examinations, ECGs, performance status assessments, and clinical laboratory parameters.

Planned time points for all safety assessments are provided in the SoA (Section 1.3).

8.3.1 Physical examinations, height, and body weights

Physical examinations will be performed (by inspection, palpation, and auscultation) by a physician or advanced practice provider (i.e., certified nurse practitioner or physician's assistant) at the trial site according to the SoA (Section 1.3).

A complete physical examination will include, at a minimum, assessments of the cardiovascular, respiratory, gastrointestinal, and neurological systems.

An abbreviated physical examination (a limited, symptom-directed physical examination) will be performed at the other times noted in the SoA and as clinically indicated at other time points. New or worsened clinically significant abnormalities will be recorded on the AE page of the eCRF.

Height (in cm) and weight (in kg) will be assessed at screening. Weight will be assessed at additional time points as indicated in the SoA. Assessment of weight should be repeated at any time if there are apparent weight changes.

Investigators should pay special attention to clinical signs related to previous serious illnesses.

Page 75 of 127 Version: 2.0 Date: 22 JAN 2024

Any untoward physical examination findings that are identified during the active collection period and meet the definition of an AE or SAE (see Sections 10.4.1 and 10.4.2) must be reported according to the processes in Sections 10.4.3 and 10.4.4.

8.3.2 Vital signs

Vital signs (oral body temperature (in °C), systolic/diastolic blood pressure, heart rate, and respiratory rate) will be assessed at the time points listed in Section 1.3).

The same position and methods for measuring the vital signs should be used for one trial patient throughout the trial.

Vital signs measurements should be preceded by at least 10 minutes of rest for the trial patient in a quiet setting without distractions (e.g., television, cell phones). Vital signs will be measured with trial patients in the seated position and before any blood draws.

Blood pressure and pulse measurements will be assessed with a completely automated device. Manual techniques will be used only if an automated device is not available.

If vital signs measurements are abnormal, two further measurements must be done at intervals of 1 min and the average of the three measurements must be recorded on the eCRF.

Any untoward vital signs findings that are identified during the active collection period and meet the definition of an AE or SAE (see Sections 10.4.1 and 10.4.2) must be reported according to the processes in Sections 10.4.3 and 10.4.4.

8.3.3 Electrocardiograms

Planned time points for ECGs are provided in the SoA (Section 1.3).

If cardiac symptoms occur, during an AE the site should perform an unscheduled ECG to confirm/diagnose the event.

Triplicate/ 12-lead ECG will be recorded as outlined in the SoA using an ECG machine that automatically calculates the ventricular heart rate and measures PR, QRS, QT, and QTcF intervals. Refer to Section 7 for QTc withdrawal criteria and any additional QTc readings that may be necessary.

Triplicate ECG readings should include three individual ECG tracings obtained as closely as possible in succession, but no more than 2 min apart. The full set of triplicates should be completed in less than 4 min.

8.3.4 Clinical laboratory tests

Planned time points for biosampling for clinical laboratory tests are provided in the SoA (Section 1.3).

The below listed clinical laboratory parameters will be assessed. Blood sampling and urine collection for additional clinical laboratory tests (including the addition of parameters) may be performed at any time during the trial as determined necessary by the investigator or required by local regulations.

Page 76 of 127 Version: 2.0 Date: 22 JAN 2024

The planned clinical laboratory parameters include:

- Chemistry: to include sodium, potassium, chloride, bicarbonate, blood urea nitrogen, creatinine, glucose, calcium, phosphate, magnesium, AST, ALT, total bilirubin, alkaline phosphatase, total protein, albumin, and uric acid. Estimated glomerular filtration rate (eGFR) will be calculated.
- Hematology: hemoglobin, hematocrit, red blood cell count, white blood cell count and differential (neutrophils, lymphocytes, monocytes, eosinophils, basophils), platelet count, MCV and MCH.
- Serum amylase, -lipase, GGT, and haptoglobin.
- Dipstick urine analysis: glucose, bilirubin, ketone, specific gravity, blood, pH, protein, urobilinogen, nitrite, and leukocyte esterase.
- Microscopic urinalysis: if warranted by dipstick results, urine sediment will be microscopically examined for the presence of red blood cells, white blood cells, casts, crystals, epithelial cells, and bacteria.
- Only in patients born female where the postmenopausal status needs to be confirmed: Follicle stimulating hormone (FSH) at signing of the ICF.
- Only for POCBP: urine
 ß-human chorionic gonadotropin (ßhCG).
- DPD and UGT1A1 genotype testing at screening if required by local regulations.

The investigator must review the laboratory report, document this review, and record any clinically relevant changes occurring during the trial as AEs in the AE section of the eCRF. The laboratory reports must be filed with the source documents. For a definition of clinically significant abnormal laboratory findings, see Section 10.4.1.3.2.

All laboratory tests with values considered clinically significantly abnormal during participation in the trial or within 14 days after the last dose of trial treatment should be repeated until the values return to normal or baseline or are no longer considered clinically significant by the investigator or the trial Medical Monitor.

If such values do not return to normal/baseline within a period of time judged reasonable by the investigator, the etiology should be identified, and the sponsor notified.

If laboratory values from non-protocol specified laboratory assessments performed at the site's local laboratory require a change in patient management or are considered clinically significant by the investigator (e.g., SAE or AE or dose modification), then the results must be recorded in the eCRF.

Any (serious) AEs resulting from laboratory tests values will be graded by the investigator.

8.3.5 Quality of life / patient-reported outcomes

Patient-reported outcome (PRO) instruments will be utilized to assess the treatment benefit, more fully characterize the safety profile of BNT321, and will enable the capture of each patient's direct experience with BNT321.

Page 77 of 127 Version: 2.0 Date: 22 JAN 2024

PRO data will be collected using European Organization for Research and Treatment of Cancer (EORTC) Quality of Life Core Questionnaire (QLQ-C30) combined with EORTC Quality of Life Questionnaire for pancreatic cancer (QLQ-Pan26). PRO instruments will be self-administered at the clinic at screening, Day 1 of every other treatment cycle starting from Cycle 3, at EOT, and at every disease assessment time point (see SoA Section 1.3) These instruments will be administered before the patient receives any information on their disease status, prior to the performance of non-PRO assessments, and prior to the administration of trial treatment.

8.3.5.1 Description of PRO assessment instruments

The EORTC QLQ-C30 is a validated and reliable self-reporting measure (Aaronson et al. 1993; Fitzsimmons et al. 1999) that consists of 30 questions that assess five aspects of patient functioning (physical, emotional, role, cognitive, and social), three symptom scales (fatigue, nausea and vomiting, pain), global health and quality of life, and six single items (dyspnea, insomnia, appetite loss, constipation, diarrhea, and financial difficulties) with a recall period of the previous week. Scale scores can be obtained for the multi-item scales. The functioning and symptoms items are scored on a 4-point scale that ranges from "not at all" to "very much," and the GHS and QoL items are scored on a 7-point scale that ranges from "very poor" to "excellent".

The EORTC QLQ-PAN26 consists of 26 questions that assess nine pancreatic cancer-related and treatment-related symptoms (pain, eating-related items, cachexia, hepatic symptoms, side effects, altered bowel habits, ascites, indigestion, and flatulence) and five emotional domains specific to pancreatic cancer (body image, healthcare satisfaction, sexuality, fear of future health, an ability to plan for the future) (Mackay et al. 2022). The QLQ-PAN26 is scored on a 4-point scale that ranges from "not at all" to "very much".

NOTE: This instrument has a current pending update which will be updated when available.

8.4 Adverse events and serious adverse events

Definitions of AEs and SAEs can be found in Section 10.4.

8.4.1 Time period and frequency for collecting AE and SAE information

All AEs/SAEs will be collected from the signing of the ICF until the safety follow-up visit at the time points specified in the SoA (Section 1.3).

Medical occurrences that begin before the start of trial treatment administration but after obtaining informed consent will be recorded on the respective Medical History/Current Medical Conditions section of the eCRF and not in the AE section.

8.4.2 Detecting and reporting AEs and SAEs

The investigator and any qualified designees are responsible for detecting, documenting, and reporting events that meet the definition of an AE or SAE and remain responsible for following up all AEs and SAEs. The investigator will record on the eCRF all observed directly, and all spontaneously reported AEs and SAEs reported by the patient.

Page 78 of 127 Version: 2.0 Date: 22 JAN 2024

Open-ended and non-leading verbal questioning of the patient is the preferred method to inquire about AE occurrences. Care will be taken not to introduce bias when detecting AEs and/or SAEs.

The recording, evaluating, and assessing of AEs and SAEs are provided in Section 10.4.

For grading the intensity of AEs and SAEs, Version 5 of the US National Cancer Institute Common Terminology Criteria for Adverse Events (NCI CTCAE) will be used.

Investigators are not obligated to actively seek AE or SAE after conclusion of the trial participation. However, if the investigator learns of any SAE, including a death, at any time after a patient has been discharged from the trial, and they consider the event to be related (see Section 10.4) to the trial treatment or trial participation, the investigator must promptly notify the sponsor as described in Section 10.4.4.

The investigator may be requested by the sponsor to obtain specific follow-up information in an expedited fashion.

All SAEs (initial and follow-up reports) will be recorded and reported to the sponsor or designee within 24 h after the site becoming aware of the event, as indicated in Section 10.4.4.

8.4.3 Follow-up of AEs and SAEs

After the initial AE/SAE report, the investigator is required to proactively follow each patient at subsequent visits/contacts. All AEs and SAEs will be followed until resolution, stabilization, the event is otherwise explained, or the patient is lost to follow-up (as defined in Section 7.3). Further information on follow-up procedures is provided in Section 10.4.2.2.

The investigator is obligated to perform or arrange for the conduct of supplemental measurements and/or evaluations as medically indicated or as requested by the sponsor to elucidate the nature and/or causality of the AE or SAE as fully as possible. This may include additional laboratory tests or investigations, histopathological examinations, or consultation with other health care professionals.

New or updated information will be recorded in the originally completed eCRF.

If a patient dies during participation in the trial or during the follow-up period (see the SoA in Section 1.3), the investigator will provide the sponsor a copy of any postmortem findings including histopathology.

The investigator will submit any updated SAE data to the sponsor within 24 h of receipt of the information.

All ongoing AEs/SAEs will be followed until resolution, considered by the investigator to be stable or chronic (resolved with sequelae), the patient is lost to follow-up or the patient withdraws consent. If no final status is reached at the EOT visit, the investigator must confirm the unavailability of a final status.

Page 79 of 127 Version: 2.0 Date: 22 JAN 2024

8.4.4 Reporting requirements for SAEs including SUSARs

Prompt notification of an SAE via EDC and/or the provided SAE form by the investigator to the sponsor within 24 hours of the site awareness is essential so that the ethical responsibilities toward patients, the safety of the trial treatment under clinical investigation, and regulatory reporting obligations can be met.

The sponsor has a legal responsibility to notify both the local regulatory authority and other regulatory agencies involved in the conduct of trials with the same IMP about the safety of a trial treatment under clinical investigation. The sponsor will comply with country-specific regulatory requirements relating to safety reporting to the regulatory authority, Institutional Review Boards (IRBs)/Independent Ethics Committees (IECs), and investigators. The execution of reporting to the different entities may be delegated as detailed in the trial-specific Safety Management Plan.

All serious adverse reactions, the nature, intensity, or outcome of which is not consistent with the reference safety information are "unexpected serious adverse reaction". The expectedness assessment for all related SAEs is based on the reference safety information included in Section 6.2 of the BNT321 IB.

All suspected adverse reactions related to an IMP (the tested drugs and comparators) that occur in this trial, and that are both unexpected and serious are qualify as suspected unexpected serious adverse reactions (SUSARs). SUSARs are subject to expedited reporting requirements according to applicable regulatory requirements and guidance (e.g., ICH E2A guidance).

For the IMPs, it is the sponsor's or delegate's responsibility to perform expedited SUSAR reporting submission to the applicable regulatory authorities, the IRBs/IECs within the timelines stipulated in the respective country regulations. Reporting to the investigators will follow country-specific regulatory requirements and applicable guidelines.

All AEs suspected to be related to the AxMP should be sent by the investigator to the national competent authority in the country where it occurred (according to the national legislation) or to the marketing authorization holder of the AxMP, but not to both, to avoid duplicate submissions (ENTR/CT-3, GVP Module VI EMA/873138/2011 Rev 2).

An investigator who receives an investigator safety report describing an SAE or other specific safety information (e.g., summary or listing of SAEs) or SUSARs from the sponsor should review it and then file it together with the IB. If required by local requirements, the investigator will notify the relevant IRB/IEC.

8.4.5 Pregnancy counseling, testing, and collection of pregnancy information For POCBP, pregnancy tests and counseling will be performed at the times given in the SoA (Section 1.3).

Any trial patient who becomes pregnant while participating in the trial will be immediately permanently discontinued from trial treatment.

For the details about the collection of pregnancy information, see Section 10.5.3.

Page 80 of 127 Version: 2.0 Date: 22 JAN 2024

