The Phase I, dose escalation part of this trial will be a limited evaluation of two planned BNT321 dose levels in combination with mFOLFIRINOX chemotherapy (24 weeks) followed by BNT321 monotherapy (24 weeks). Following determination of the combination recommended Phase II dose (RP2D), the Phase II (randomized treatment) part of this trial will be initiated as an open-label 2-arm evaluation of mFOLFIRINOX ± BNT321 (24 weeks) followed by BNT321 monotherapy (24 weeks) in the combination arm only to complete the adjuvant therapy course. Treatment cycles are every 2 weeks (14 days).

The primary endpoint for the Phase I part of this trial is characterization of the safety and RP2D of BNT321 in combination with mFOLFIRINOX. The primary endpoint for Phase II of this trial is to assess the efficacy of mFOLFIRINOX + BNT321 versus mFOLFIRINOX alone as adjuvant therapy in PDAC patients post R0 or R1 resection by DFS.

Safety monitoring assessments will be performed 28 days after the last dose of BNT321. Information on survival follow-up, new anticancer and cancer-related procedures will be collected for all patients via telephone calls, patient medical records, and/or clinic visits from BNT321

^{**} RCP classification. Tumors designated R0 CRM+ (R0 narrow) according to CRM concept will be stratified as R1 tumor in this trial.

Page 6 of 127 Version: 2.0 Date: 22 JAN 2024

treatment discontinuation and approximately every 12 weeks until 5 years (unless the patient withdraws consent, or the sponsor terminates the trial).

For a detailed summary of Phase I and Phase II design, see Section 4.1.1 and 4.1.2, respectively.

For a summary of the trial as a flow diagram, see the Schema in Section 1.2.

For the planned assessments and visits, see the Schedule of Activities (SoA) in Section 1.3.

Duration of the trial periods

For both Phase I and Phase II, there will be a screening period of 21 days.

Phase I will consist of ~48 weeks of therapy, with 24 weeks of mFOLFIRINOX + BNT321 combination therapy followed by 24 weeks of BNT321 monotherapy. Phase II will be a randomized 2-arm trial, with 48 weeks of treatment in the combination arm (mFOLFIRINOX + BNT321) and 24 weeks of therapy in the control arm (mFOLFIRINOX only).

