For both Phase I and Phase II, there will be a safety follow-up of 28 days ± 14 days after the last dose of trial treatment. DFS status will be recorded every 3 months for 2 years and then every 6 months for the next 3 years. Overall survival status will be recorded up to 60 months.

The maximum trial duration for each phase is ~5 years after the last patient's first treatment in the trial.

Trial population

This trial will enroll patients aged >18 years or of an age deemed to be an adult per local authorities with recently resected PDAC considered appropriate for adjuvant treatment with mFOLFIRINOX. All enrolled patients must meet the trial eligibility criteria listed in Section 5.

Number of patients

A maximum of 320 patients will be included in this trial. Approximately 20 patients will be enrolled into the Phase I part with BNT321 in combination with mFOLFIRINOX. Approximately 300 patients will be randomized at 1:1 into the Phase II part with BNT321 in combination with mFOLFIRINOX or mFOLFIRINOX only.

Trial treatments

Name	mFOLFIRINOX	BNT321
Trial treatment type	Chemotherapy	Monoclonal antibody
Dosage form	NA	BNT321 is provided as a single-use glass vial containing 8.0 mL of sterile solution
Unit dose strength(s)	 Oxaliplatin: 85 mg/m² Leucovorin: 400 mg/m² Irinotecan: 150 mg/m² 5-FU: 2400 mg/m²* 	0.5 CI mg/kg based on cohort

Page 7 of 127 Version: 2.0 Date: 22 JAN 2024

[figure not shown]
Name	mFOLFIRINOX	BNT321
Dosage regimen	mFOLFIRINOX will be administered on the first day of each 14-day cycle (i.e., C1D1, C2D1, C3D1, and so on for a total of 12 cycles) using the following dose and schedule for each agent: Oxaliplatin: Day 1 Leucovorin: Day 1 Irinotecan: Day 1 (starting	BNT321 will be incorporated into the mFOLFIRINOX regimen starting from the second cycle and after the completion of the 5-FU infusion (e.g., initially on C2D3).
	30 minutes after leucovorin) • 5-FU: Day 1	
Diluent	mFOLFIRINOX is prepared and administered according to institutional standards, in compliance with the package insert for each drug	
Route of administration	 Oxaliplatin: IV over 2 hours Leucovorin: IV over 2 hours Irinotecan: IV over 90 minutes 5-FU: Continuous IV infusion over 46 hours, following oxaliplatin, leucovorin, and irinotecan 	IV infusion
Sourcing	See the Pharmacy Manual	See the Pharmacy Manual
Packaging and labeling	For details see the Pharmacy Manual	For details see the Pharmacy Manual

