2.3 Benefit/risk assessment

For BNT321 detailed information about the known and expected benefits and risks including expected AEs are also detailed in the BNT321 IB.

Additional information regarding the expected risks, including expected AEs for mFOLFIRINOX are provided in the product labels or summaries of product characteristics (SmPCs) for the individual agents of this regimen.

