4.2.2 Trial design rationale for Phase II: Randomized mFOLFIRINOX ± BNT321

The randomized Phase II part of this trial is designed as a dedicated evaluation of the potential for BNT321 combination therapy with mFOLFIRINOX to provide meaningful clinical benefit to patients with R0 or R1 surgically resectable PDAC. mFOLFIRINOX, the selected regimen for combination and the comparator arm for BNT321-02, is considered a superior option to gemcitabine + nab-paclitaxel for PDAC adjuvant therapy based on results of Phase III PRODIGE 24 and APACT studies (Conroy et al. 2018 and Tempero et al. 2022 respectively). The BNT321-02 Phase II design employs several parameters from the pivotal Phase III PRODIGE 24 study.

DFS is selected as the primary endpoint for the randomized Phase II part of this trial. This is an established, clinically meaningful outcome previously used as primary endpoint in the PRODIGE 24 and APACT Phase III trials. A substantial improvement in mDFS is sought in trial BNT321-02, specifically a greater than 12 months increase with the introduction of Q2W BNT321 to the 24-week mFOLFIRINOX chemotherapy standard (target 36 vs 21.6 months DFS, hazard ratio [HR] 0.60).

In addition to primary endpoint mDFS, additional outcome measures evaluated as secondary endpoints include 12 months DFS and OS at 24 months. The mFOLFIRINOX 12 months DFS rate of 69.0% observed in PRODIGE 24 is a high efficacy benchmark, but a significant DFS improvement at this timepoint in BNT321-02 would represent a major efficacy advance and may be a consideration for accelerated registration. Overall survival assessment at 24 months is in a feasible timeframe relative to the trial mDFS primary endpoint and may provide additional supportive efficacy data in this first BNT321 adjuvant trial.

The randomized Phase II part of this trial will be conducted in an open-label fashion, consistent with design of other major adjuvant studies (Tempero et al. 2022). Another notable design consideration is inclusion of stratifications for surgical resection status (R0 versus R1) and nodal status at time of resection (pN0 versus pN1). Both of these resection characteristics are recognized as significant factors in clinical outcome in resected PDAC and so are justified for stratification in the BNT321-02 trial design, similar to an approach in previous PDAC adjuvant studies (Conroy et al. 2018).

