6 TRIAL TREATMENTS AND CONCOMITANT THERAPY

Trial treatment is defined as any investigational treatment(s), marketed product(s) used as auxiliary medicinal product (AxMP) intended to be administered to a patient according to the trial protocol.

An "IMP" is any medicinal product which is being tested or used as a reference in a clinical trial (the tested product and its reference products, including placebos).

An "AxMP" is a medicinal product used for the needs of a clinical trial as described in the protocol, but not as an IMP (medicinal products used in the context of a clinical trial but not as investigational medicinal products).

Concomitant therapy is not considered trial treatment.

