- Not related (= there is no reasonable possibility of a causal relationship)

Page 114 of 127 Version: 2.0 Date: 22 JAN 2024

The relationship or association of an AE or SAE to a trial treatment/trial procedure will be assessed by the investigator after having evaluated all accessible data and, if necessary, the investigator will re-evaluate the case as new information becomes available.

Events caused by the procedure of trial treatment administration should be differentiated from events caused by the trial treatment itself. Only events suspected to be caused by the IMPs itself should be documented as suspected adverse reactions but not events caused by the AxMP or the procedure of trial treatment administration.

In this trial, it cannot be excluded that during the course of the trial some procedures give rise to AEs which are related to the trial procedure and not to the trial treatment. Procedure-related AEs can occur on the site of injection of the trial treatment (e.g., redness, swelling, hematoma or itching) or during or after trial-specific procedure (e.g., discomfort after blood drawing). These events must be reported in the eCRF on Adverse Event pages as "related to trial procedure" with the causing procedure specified. The intensity of these AEs will be characterized according to the NCI CTCAE v5.0

Relationship to trial treatment

- The relationship or association of an AE or SAE to a trial treatment (either BNT321 or mFOLFIRINOX) will be made by the investigator after having evaluated all accessible data and, if necessary, he/she will re-evaluate the case as new information becomes available.
- Events caused by the procedure of trial treatment administration should be differentiated from events caused by the trial treatment itself. Only events suspected to be caused by the IMPs itself should be documented as suspected ARs but not events caused by the AxMP or the procedure of trial treatment administration.

Notes applicable for initial reporting of SAEs where the investigator has minimal information available

There may be situations in which an SAE has occurred, and the investigator has minimal information to include in the initial report to the sponsor. However, it is very important that the investigator always makes an assessment of causality for every event before the initial transmission of the SAE data to the sponsor.

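### Section 8.4.4 judges expectedness of all related SAEs against the BNT321 brochure only, although comparator reactions are also SUSAR candidates

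*Combined protocol and SAP*

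**What the plan says.** Section 8.4.4 sets the reference for expectedness in one sentence: "The expectedness assessment for all related SAEs is based on the reference safety information included in Section 6.2 of the BNT321 IB". It names no other reference safety information and makes no exception for the control arm.

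The next paragraph defines the pool from which SUSARs are drawn: "All suspected adverse reactions related to an IMP (the tested drugs and comparators) that occur in this trial", provided that they are both serious and unexpected.

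Section 10.4.3 makes causality a question about the chemotherapy as well as the antibody: "The relationship or association of an AE or SAE to a trial treatment (either BNT321 or mFOLFIRINOX) will be made by the investigator".

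Section 2.3 sends the reader elsewhere for the chemotherapy: "expected AEs for mFOLFIRINOX are provided in the product labels or summaries of product characteristics". It does so as benefit/risk background, and Section 8.4.4 does not refer to it.

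**The concern.** Expectedness is a property of a product: the question is whether the event is already listed for the drug suspected of causing it. Section 8.4.4 admits reactions to two treatments into the SUSAR definition but supplies a list for one. A control patient can have a serious reaction attributed to mFOLFIRINOX, and the rule then compares it with the brochure of a drug that the patient never received. The same happens in the combination arm when an event is attributed to the chemotherapy alone.

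Expedited reports go to regulators, ethics committees and investigators. An error can run in either direction:

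- A reaction listed on a chemotherapy label but not in the brochure would be expedited as unexpected.
- A reaction listed in the brochure but not on the chemotherapy label would be treated as expected and not expedited.

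**Working it through.** No figure in the plan bears on this point, so there is nothing to reproduce. The check sets the passages side by side and then gives a sense of scale.

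**Step 1. Is mFOLFIRINOX inside the SUSAR definition?**

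- Section 6 defines an IMP as "any medicinal product which is being tested or used as a reference in a clinical trial".
- Section 4.2.2 describes "mFOLFIRINOX, the selected regimen for combination and the comparator arm for BNT321-02".
- Section 8.4.4 counts comparators among the IMPs for SUSAR purposes.
- Section 10.4.3, under assessment of causality, requires relatedness to be judged for the IMP and for the comparator product.
- Section 9.4 admits to the Safety Analysis Set only patients who received at least one dose of IMP. Control patients qualify only if mFOLFIRINOX is an IMP.

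Together these passages favour IMP status, although no passage states it.

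**Step 2. Which SAEs are affected?** The expectedness sentence covers all related SAEs. Under Section 10.4.3, an SAE related only to mFOLFIRINOX is a related SAE. It therefore falls under the rule and is compared with Section 6.2 of the BNT321 brochure.

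**Step 3. How many patients?** The Synopsis states: "Approximately 300 patients will be randomized at 1:1 into the Phase II part". At 1:1 allocation, 300 / 2 = 150 control patients. They receive mFOLFIRINOX alone for 24 weeks (Section 4.1.4), so any treatment-related SAE among them is mFOLFIRINOX-related.

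**Step 4. Do the two lists differ?** The lists themselves are not in the documents. Table 5 is the nearest evidence:

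- Under mFOLFIRINOX only: hematological changes, mucositis, cardiac toxicity, sensory peripheral neuropathy.
- Under BNT321 only: infusion-related reactions.
- Under both: liver function changes and gastrointestinal events, including diarrhea.

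This suggests different lists but does not prove it. For example, Section 2.3.2 reports peripheral sensory neuropathy (33.3%) and stomatitis (26.7%) in the 15 patients who received the combination in the earlier Phase I trial, so the brochure may mention such events.

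**Step 5. Scale.** Section 2.3.2 quotes Grade 3 or 4 rates for adjuvant mFOLFIRINOX from the cited Phase III trial. Applied to 150 control patients:

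- Neutropenia: 150 × 0.284 = 42.6, about 43 patients.
- Sensory peripheral neuropathy: 150 × 0.093 = 13.95, about 14 patients.
- Febrile neutropenia: 150 × 0.03 = 4.5, 4 to 5 patients.

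Grade 3 or 4 does not mean serious, and the brochure list is unknown. These figures show that chemotherapy toxicity will be common in the control arm. They are not SUSAR counts.

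**The case against.** The strongest reply is that mFOLFIRINOX may be an AxMP. Section 6 counts marketed products used as AxMPs among trial treatments. Section 8.4.4 ends with a separate route for AxMP-related events, to the national authority or the marketing authorization holder. Section 10.4.3 excludes events caused by an AxMP from suspected adverse reactions. Several places use IMP for BNT321 alone: the title of Section 2.2.2, the PK endpoint in Section 3, and the death criterion in Section 6.3.5. On that reading a single BNT321 list would be coherent.

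Part of this stands: the regulatory status of mFOLFIRINOX is not stated, and a fix should not presume it. It does not rescue the sentence. No passage designates mFOLFIRINOX an AxMP, and the phrase about all related SAEs has no AxMP exception. If BNT321 were the only IMP, control patients would fall outside the Safety Analysis Set, and the Phase II safety endpoint, defined in patients given IMP, would have no control group. The wording needs to change on either reading.

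A second reply is that other safeguards exist, and this is fair. SAEs reach the sponsor within 24 hours whatever their expectedness (Sections 8.4.2 and 10.4.4). The IDMC reviews unblinded safety data at least twice a year, and in Phase I every related SAE triggers an SRC review (Section 10.1.5). Phase II is open-label. These limit the harm of a misclassified report but do not correct the classification. Section 8.4.4 cites the Safety Management Plan only for delegating the execution of reporting, not for choosing the reference document.

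A reader might also try to count false SUSARs, for instance from Grade 3 or 4 diarrhea at 18.6% (150 × 0.186 = 27.9 patients) and an assumed serious fraction. The documents do not support this. Table 5 lists diarrhea among the BNT321 gastrointestinal risks, so the brochure may well list it, and no serious fraction is given.

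**Conclusion.** The expectedness rule does not fit the scope of the SUSAR definition that follows it. Followed literally, it classifies SAEs related only to mFOLFIRINOX, including all treatment-related SAEs in about 150 control patients, against the reference list of another drug. The rule names the wrong reference for these events; it is more than a missing detail.

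A reader might infer that SUSARs will be misidentified in known numbers, or that true signals will be missed. The documents show only that misclassification is possible. For the missed-signal direction, an event would have to be listed in the brochure and absent from the chemotherapy labels. Infusion-related reactions are a candidate from Table 5, but the labels are not available to confirm it.

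The conclusion assumes that mFOLFIRINOX is an IMP, the reading best supported by the definitions, the comparator wording and the safety set. If it is an AxMP, the defect shifts to the unqualified sentence and the conflicting IMP-based definitions. The issue concerns safety reporting; the DFS analysis and the sample size do not change.

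**What to change.** State in Section 6 whether mFOLFIRINOX is an IMP or an AxMP, and align Section 8.4.4 accordingly.

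- **If IMP:** limit the Section 6.2 brochure reference to BNT321-related SAEs. Name the designated SmPC or label(s) as reference safety information for mFOLFIRINOX-related SAEs. Assess an event attributed to both against each reference. Specify which regional label applies, since Table 7 shows that US and EU texts can differ. Section 10.4.3 asks for causality to the regimen as a whole, so also say how the component labels are used together; attribution to single components is not currently required.
- **If AxMP:** limit the expectedness sentence to BNT321-related SAEs. Reconcile the comparator wording in Section 8.4.4, the Safety Analysis Set in Section 9.4 and the Phase II safety endpoint in Section 3, so that control patients remain covered.

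The cost is a short edit to the protocol and the Safety Management Plan, somewhat wider in the AxMP case because the safety definitions must also be revised.
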